1 **Effects of Predialytic Exercise Training and Detraining on Physical Fitness and Inflammation in Hemodialysis Patients**

2

3 **NCT05649657**

4 **July, 15th, 2020**

5

6 **1. Introduction**

7 Patients receiving maintenance hemodialysis (HD) account for over 0.04% of the global population and contribute to an increasing burden on healthcare
8 systems [1]. Among individuals under maintenance HD, physical fitness deterioration and chronic fatigue are well- documented conditions [2]. Notably, low
9 cardiorespiratory fitness (CRF) and sarcopenia are significant predictors of cardiovascular events and mortality [3, 4], and are also associated with reduced
10 health-related quality of life (QOL) [5]. Patients on maintenance HD are generally sedentary [6]; and exercise therapy has been suggested to improve
11 cardiovascular morbidity and mortality in this population [7].

12 Regarding the timing of exercise training, two approaches are commonly used: exercise during hemodialysis (HD) and on non-HD days. The protocols of
13 the former primarily consist of supine or seated exercises, such as aerobic cycling or resistance exercises using Thera-bands or weighted ankle cuffs [8].
14 Exercise training on non-dialysis days offers advantages, including unrestricted upper limb movement, higher-intensity training, and a lower risk of catheter
15 dislodgement, bleeding, and hypotension. However, hospital-based protocols on non-HD days exhibited a higher dropout rate [9].

16 Only a few studies have investigated hospital-based exercise training prior to hemodialysis (HD). To the best of our knowledge, five such studies have
17 been reported. Of these, four focused exclusively on resistance training (RT) [10-13], while the fifth examined a virtual reality program with diverse exercise
18 modalities [14]. None of the studies investigated a structured program combining cyclic aerobic and resistance training, nor did they conduct any evaluation
19 after a period of time following training discontinuation. Additionally, only one study assessed the effects of training on systemic inflammation [13]. Please
20 refer to the Discussion for details.

21 Hemodialysis patients often exhibit chronic inflammation, impairing muscle protein synthesis and affecting body composition and function [15]. While
22 exercise may reduce inflammation [16], the effect of pre-dialytic exercise—performed in a hypervolemic state—on systemic inflammation, either positively or
23 negatively, remains unclear.

24 This study aimed to evaluate the effects of pre-dialytic exercise conducted 1–2 hours before HD (PDE) on muscular and cardiorespiratory fitness, QOL,
25 and inflammatory cytokines. A within-subject design included a 3-month control, 6-month training, and 3-month follow-up. We hypothesized that PDE would
26 improve CRF, quadriceps strength, body composition, QOL and systemic inflammation. Gold-standard measurements of physical fitness including body
27 composition analysis using dual-energy x-ray absorptiometry (DXA), isokinetic dynamometry (isok) and cardiopulmonary exercise test (CPET) were
28 employed. Additionally, a 3-month post-training follow-up assessed carry-over effects.

29

30 **2. Materials and Methods**

31 **2.1. Study protocol**

32 Participants were eligible for inclusion if they had been undergoing HD for more than 3 months, were over 20 years of age, had adequate dialysis ($Kt/V >$
33 1.2), obtained approval from their nephrologist, and were able to walk independently for more than 10 meters. Exclusion criteria included recent hyperkalemia,
34 medical or orthopedic conditions, muscular or psychological disorders, and a history of heart failure or inability to participate in cycling or exercise testing.
35 This study was approved by the Chang Gung Medical Foundation Institutional Review Board. It was conducted between July 2020 and February 2025. All

36 participants provided written informed consent after the researchers explained the experimental procedures. The study complied with the tenets of the
37 Declararation of Helsinki.

38 This study employed self-controlled design. Over the study period, each participant underwent assessments at five time points (T1, T2, T3, T4, and T5) with
39 about 3 months between each time point. Between T1 and T2 was the control phase, the participants received usual medical care only. Between T2 and T4 was
40 the training phase, exercise training and nutrition education were implemented. The T4–T5 follow-up phase monitored changes after training cessation with
41 standard medical care only (Fig 1).

42 The assessment involved CPET, isok, hand grip strength (HGS), DXA, mini-nutritional assessment (MNA), generic and CKD-specific quality of life (Kidney
43 Disease Quality of Life, KDQOL), International Physical Activity Questionnaire (IPAQ), plasma inflammatory cytokine and white blood cell differential counts
44 (Fig 1).

45 **2.2. Exercise training program**

46 Before training, an exercise physiologist assessed safety risk profiles and provided an exercise prescription. Then, it was carried out by a properly trained
47 physical therapist. Contraindications for exercise training primarily followed the guidelines of the American College of Sports Medicine. Common conditions
48 included a resting sinus heart rate > 100 bpm and blood pressure > 180/110 mmHg [17]. Blood pressure and ECG were monitored throughout each session. The
49 participants visited the rehabilitation center twice or three times weekly and about 72 sessions in total, which lasted between 24 and 36 weeks. The exercise
50 prescription comprised cyclic aerobic and resistance training. The training was performed 1-2 hours before HD. Cycle ergometry (Lode Corival V3), recumbent
51 stepper (Nustep) and treadmill (Biomed) were used. The intensity was set initially at ventilatory anaerobic threshold (VAT) based on CPET. The duration was 30

52 minutes per session plus 3-minute warm-up and 3-min cool-down. Once the patient was able to tolerate intensity at VAT for 20 minutes continuously, high-
53 intensity interval training (HIIT) was implemented. The training intensity was given initially at 40% peak work rate (low) for 2 minutes and followed by 80%
54 peak work rate (high) for another 2-min interval. The intensity changed repeatedly at high and low intensity throughout the session. Brief pauses were allowed
55 during a single training session. If the patient could complete a single session without any pause, the high intensity of HIIT was adjusted to increase 5% (for
56 example, 80% to 84%) [18]. Additionally, cyclic RT was performed using isokinetic training system (BodyGreen). Eight devices were applied: leg press, thigh
57 adduction/abduction, leg extension/curl, shoulder press/pull down, pec dec/fly, wait twist, chest press/seated rowing. In each session, three devices were adopted.
58 Ten repetitions were performed with maximal volitional effort in each device.

59 Please refer to S1 for detailed information on methodology. **2.3.** Nutrition Program; **2.4.** Cardiopulmonary exercise testing; **2.5.** Body composition; **2.6.**
60 Isokinetic dynamometry; **2.7.** Hand grip strength; **2.8.** Hong Kong Chinese Kidney Disease Quality of Life; **2.9** International Physical Activity Questionnaire
61 (IPAQ); **2.10.** Measurement of plasma inflammatory cytokines and white blood cell differential counts.

62 **2.11. Statistics**

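### Nutrition education and a post-session protein supplement are delivered only alongside the exercise, so no pairwise stage comparison isolates pre-dialytic exercise, or its withdrawal

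*Combined protocol and SAP*

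**What the plan says.** The title is "Effects of Predialytic Exercise Training and Detraining on Physical Fitness and Inflammation in Hemodialysis Patients". The Introduction gives the aim in the words "This study aimed to evaluate the effects of pre-dialytic exercise conducted" and then the timing relative to dialysis. It hypothesises that this exercise would "improve CRF, quadriceps strength, body composition, QOL and systemic inflammation", and adds that "a 3-month post-training follow-up assessed carry-over effects". Nutrition appears in none of these statements.

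Section 2.1 sets out the design: "This study employed self-controlled design", with five visits about three months apart. In the control phase (T1–T2) "the participants received usual medical care only". In the training phase (T2–T4) "exercise training and nutrition education were implemented". In the follow-up phase (T4–T5) training has ceased and care is again ordinary medical care with nothing added.

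Supplement S1, section 2.3, describes the nutrition programme. It begins once the T2 assessment is done, with a 7-day food record, a dietitian's assessment and individual food-based advice. Each participant keeps a logbook, and the dietitian follows how well the advice is kept. A commercial high-protein supplement is handed out at the end of every training session. Section 2.2 puts the number of sessions at about 72, over 24 to 36 weeks.

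Section 2.11 names one analysis: a repeated-measures mixed model with stage (T1 to T5) as the only fixed effect mentioned, followed by pairwise comparisons.

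**The concern.** The question is posed about exercise and the intervention is a package. Dietary advice and extra protein start at the same boundary as exercise. The supplement is tied to the sessions, so it also stops with them. If an outcome improves between T2 and T4, the data cannot show whether exercise, advice, supplement or a mixture produced the change. If it falls between T4 and T5, the data cannot show whether that reflects lost training or lost nutritional support.

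The T1–T2 control phase does not help here. It informs time trend and retest effects, but it contains none of the three components. A significant contrast reported in the terms of the hypothesis would therefore support a claim about exercise that the design cannot bear.

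**Working it through.** The documents give no figure to reproduce on this point. The check is whether any planned comparison can isolate exercise.

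**Delivery by phase** (sections 2.1 and 2.2; S1 section 2.3):

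| Interval | Exercise | Nutrition education | Supplement |
|---|---|---|---|
| T1–T2 | no | no | no |
| T2–T3 | yes | yes | yes |
| T3–T4 | yes | yes | yes |
| T4–T5 | no | no (inferred) | no |

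The three columns are identical, so delivery is completely aliased. The entry marked inferred rests on the description of T4–T5 as ordinary care; the documents do not state outright that dietitian monitoring stopped at T4. If it continued, T4–T5 would hold education fixed, but the supplement would still stop with training.

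**The pairwise comparisons.** Five visits give 5 × 4 / 2 = 10 pairs. Let E, N and S be the effects of exercise, education and supplement, taken as additive, at visits 3, 4 and 5, and write P3 = E3 + N3 + S3, and likewise P4 and P5. Apart from time trend, the pairs estimate:

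- T1–T2: no programme effect (1 pair)
- T1–T3 and T2–T3: P3 (2 pairs)
- T1–T4 and T2–T4: P4 (2 pairs)
- T1–T5 and T2–T5: P5 (2 pairs)
- T3–T4: P4 − P3 (1 pair)
- T3–T5: P5 − P3 (1 pair)
- T4–T5: P5 − P4 (1 pair)

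The total is 1 + 2 + 2 + 2 + 1 + 1 + 1 = 10. Every pair depends only on the sums P3, P4 and P5; none contains an E term without its N and S partners. Using T1–T2 to remove a linear trend changes none of this.

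**Could carry-over assumptions separate them?** Suppose each effect is the same at T3 and T4, and that fractions q, p and r of E, N and S remain at T5. Then P3 = P4 = E + N + S and P5 = qE + pN + rS. Even with q, p and r supplied, that is two equations for three unknown effects.

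Leave education out, and set r = 0 with q above 0. Now P5 = qE, so E = P5/q and S = P4 − P5/q. Exercise and supplement do separate, but the answer is driven by the assumed q: moving q from 0.5 to 1 halves the effect credited to exercise, and moving it from 0.25 to 1 divides it by four. The follow-up is itself meant to assess carry-over, so q cannot be taken as known.

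**Amount of supplement provided.** At about 72 sessions, provision is 72/36 = 2.0 to 72/24 = 3.0 per week. The documents do not give its protein content or say how much was consumed. They also do not say that the intake advice differs from usual care. The nutrition share therefore cannot be computed.

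**The case against.** The strongest defence is that nothing is hidden. Section 2.1 names nutrition education in the same sentence as training, section 2.2 points to the nutrition programme, and S1 describes it in detail. The text never says exercise alone or detraining alone, and its description of T4–T5 as follow-up after training ceases is already close to neutral. The Introduction also refers to a Discussion that is not among the documents, so a stated limitation can be neither confirmed nor excluded. All of this is fair. It limits the point to the title, aim and hypothesis as written; it does not make their attribution to exercise correct.

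A second defence is that nutritional data exist: the mini-nutritional assessment, the food record and the logbook. They can be shown descriptively. They do not remove the aliasing, because the supplement is given only after sessions, and section 2.11 names no such covariate.

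Three stronger readings are tempting and should be resisted.

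- A reader might infer that supplement and exercise can never be separated under any model. The working shows otherwise once exercise carry-over is assumed; what holds is that their delivery is aliased and that separation rests on an untestable assumption.
- A reader might count the affected comparisons and treat the count as a size. Six pairs differ in exercise delivery if each visit is coded by the interval before it; eight span an exercise interval. The number depends on the coding and measures no bias.
- A reader might rank outcomes by how far nutrition could explain them. The documents give no basis for such a ranking.

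**Conclusion.** The concern holds as a point about attribution. Exercise, nutrition education and supplement are co-delivered in T2–T4 and, on the inference above, absent from the other two phases. None of the 10 stage comparisons isolates exercise, and T4–T5 does not isolate detraining. The result follows from the delivery schedule and does not depend on sample size or effect size. Allowing interaction between components would add unknowns and would not help.

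The size of any nutrition contribution is unknown and may be small. A reader might infer that exercise had no effect, or that the study is uninformative. The documents support neither: the within-subject change under the combined programme remains estimable, subject to the usual before-after assumptions about trend and retest. The wording should be corrected before results are interpreted.

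**What to change.** Word the aim, estimand and conclusions for every contrast that spans any part of T2–T4, including T2–T5, as the within-subject change under the combined programme: pre-dialytic exercise, nutrition education and post-session protein supplement, with no concurrent control. Describe T4–T5 as the change after that programme stops, with possible carry-over. Do not attribute changes to exercise or detraining alone. State whether dietitian monitoring ended at T4. Keep the stated hypothesis on record and add a dated clarification beside it. Nutritional assessment, food-record and logbook data may be presented descriptively, with a note that they do not resolve the aliasing.

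The study is over ("It was conducted between July 2020 and February 2025"), so the change touches text only; no data collection, dataset or model is altered. The cost is a less specific claim than the title now makes.

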2.3. Nutrition Program

After T2 assessment, the participants were first required to complete an estimated food record in the past 7 days. A dietitian then conducted a nutritional assessment to provide a comprehensive evaluation and to estimate the required amount and relative proportions of macronutrients. Based on this assessment, food-based dietary advice was given. Each participant received a logbook, and adherence to the dietary recommendations was monitored by the dietitian. For dialysis patients, the recommended energy and protein intake were 25–32 kcal/kg and 1.2–1.3 g/kg of body weight, respectively [39, 40]. After each training session, the participants were provided with a commercially available high-protein supplement (Red Cow Aiji®).

2.4. Cardiopulmonary exercise testing

A symptom-limited incremental exercise test was conducted on a calibrated bicycle ergometer (Ergoselect 150P, Germany) to assess aerobic fitness. The test began with an 1-minute warm-up at 10 watts, followed by a 10-watt-per-minute increase until exhaustion, targeting 60 ± 3 revolutions per minute (rpm). Breath-by-breath minute ventilation ($\dot{V}e$), oxygen consumption ($\dot{V}O_2$), and carbonic dioxide production ($\dot{V}CO_2$) were recorded using MasterScreen CPX (Cardinal-health Germany). Heart rate, arterial pressure, and oxygen saturation were monitored using a 12-lead electrocardiogram, an automatic blood pressure system (Tango, SunTech Medical, UK), and a pulse oximeter (Nonin Onyx 9500, USA), respectively. The test ended if the participants fell below 50 rpm, reached volitional fatigue, showed a peak $\dot{V}O_2$ plateau/decline despite continued exercise, or experienced cardiovascular events. Data were averaged every 15 seconds. Ventilatory anaerobic threshold (VAT) was determined using V-slope method and confirmed by non-linearity of $\dot{V}CO_2$ vs. $\dot{V}O_2$, increased $\dot{V}e$ - $\dot{V}O_2$ ratio without a rise in $\dot{V}e$ - $\dot{V}CO_2$ ratio, and rising end-tidal oxygen without declining end-tidal carbon dioxide [41].

2.5. Body composition

This study utilized a fan-beam DXA body composition analyzer (Lunar Prodigy; GE Healthcare, Madison, WI), with data analyzed by GE Encore 12.30 software. The analyzer was calibrated before use, and scans were conducted in standard mode. Results were automatically analyzed and verified by trained professionals. Radiologists ensured participants maintained consistent posture: lying centered on the machine with foam bricks keeping their feet 15 centimeters apart and palms 3 centimeters from the torso. This process measured fat mass, muscle mass and appendicular skeletal muscle mass index (ASMI) [42].

2.6. Isokinetic dynamometry

Quadriceps peak torque (PT) was measured using a Biodex isokinetic dynamometer (System 4 ProTM; New York, NY, USA). Isometric PT (IPT) was measured at 45°, and concentric PT across a 90°–0° range. Participants exerted five maximal-effort repetitions at angular velocities of 0°/s, 60°/s, and 120°/s, with a 2-minute rest between sets. Tests with >10% variance were repeated [43]. After a 10-minute rest, participants performed a fatigue test at 120°/s, consisting of 20 maximal-effort concentric contractions. Tests with a variance greater than 15% were repeated [25]. Total work was calculated as the energy exerted during the 20 repetitions, and the fatigue index (%) measured the work decline in the final one third repetitions compared to the initial one third [44].

2.7. Hand grip strength

Hand grip strength (HGS) was measured using a dynamometer (Tsutsumi Company, Tokyo). Participants stood with palms facing their bodies, adjusting the grip for optimal force. They squeezed the dynamometer maximally for 3 seconds in two trials per hand, alternating sides. The highest value from each hand was averaged [45].

2.8. Hong Kong Chinese Kidney Disease Quality of Life

The KDQOL-SFTTM v1.3 survey was used to assess quality of life in patients with chronic kidney disease in HK, tailored for Mandarin speakers with high responsiveness in this population [46]. It includes the 11-item Short Form Health Survey and 17 kidney disease-specific items. The former covers eight categories: physical functioning, role-physical, pain, general health, emotional well-being, role-emotional, social function, and energy/fatigue, summarized into physical component summary (PCS) and mental component summary (MCS) scores. The latter covers 11 domains: symptom/problem list, effects of kidney disease, burden of kidney disease, work status, cognitive function, quality of social interaction, sleep, social support, dialysis staff encouragement, overall health, and patient satisfaction, excluding the sexual function domain [47].

2.9 International Physical Activity Questionnaire (IPAQ)

The Taiwan version of the IPAQ [48] was used to evaluate participants' physical activity levels, including vigorous, moderate, walking activities, and sitting, over the past 7 days. Participants reported their engagement in vigorous activities (e.g., running), moderate activities (e.g., light cycling), and walking for commuting or leisure, along with sitting time for desk work or TV. Total physical activity (TPA) was calculated as: (vigorous activity time \times 8) + (moderate activity time \times 4) + (walking time \times 3.3) [49].

2.10. Measurement of plasma inflammatory cytokines and white blood cell differential counts

Venous blood collection was performed by medical professionals at the hemodialysis center before hemodialysis (HD). A total of 3 mL of blood was drawn from the arteriovenous shunt of each participant and placed into tubes containing Sodium Heparin 158 USP. Plasma was separated by centrifugation at 1,300 \times g for 15 min at 4°C within one hour of collection and then stored at -80°C until analysis. Interleukin (IL)-1 beta (β), IL-6, IL-8, IL-10, IL-12p70, and tumor necrosis factor- α (TNF α) concentrations were detected in plasma using the BD Cytometric Bead Array (CBA) Human Inflammatory Cytokines Kit (Becton-Dickinson) and analyzed with FCAP ArrayTM software [50].

References

39. Kopple JD. National kidney foundation K/DOQI clinical practice guidelines for nutrition in chronic renal failure. *Am J Kidney Dis.* 2001 Jan;37(1 Suppl 2):S66-70.

